Primary Objectives	
Cohort A (Atezolizumab Monotherapy):
 
Multi-dose cohorts: To assess the intratumoral immune response associated with increasing numbers of Atezolizumab treatments.
 
Expansion cohort: To assess the anti-tumor activity of Atezolizumab as determined by the pathologic T0 rate (pT0N0) at the time of cystectomy.
 
Cohort B (Atezolizumab + Tiragolumab):
 
Multi-dose cohorts: To assess the safety of neoadjuvant combination treatment with atezolizumab and tiragolumab according to CTCAE v5.0 in cisplatin-ineligible patients with MIBC undergoing radical cystectomy.
 
Expansion cohort: To assess the anti-tumor activity of Atezolizumab + Tiragolumab as determined by the pathologic T0 rate (pT0N0) at the time of cystectomy.

Secondary Objectives	
Cohorts A & B
 
Multi-dose cohorts:
 
 1. To evaluate the safety and feasibility of administering up to 3 cycles of Atezolizumab pre-operatively to patients with resectable urothelial bladder cancer. Note this is the coprimary objective for Cohort B. 
Expansion cohort:
 
 1. To assess the anti-tumor activity of neoadjuvant treatment as determined by pathologic pathologic partial response (<pT2N0) assessed at the time of radical cystectomy 2. To determine the 2-year relapse-free survival (RFS) rate and median RFS from time of radical cystectomy in patients treated with neoadjuvant therapy 3. To determine the 2-year overall survival (OS) and median OS from time of radical cystectomy in patients treated with neoadjuvant therapy

	
 4. To assess the intratumoral immune response of neoadjuvant by comparing pre-treatment TURBT with post-treatment cystectomy tumor specimens

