2.2 Secondary Objective(s) and Endpoint(s)

Cohorts A and B

Multi-Dose Cohorts

1. To evaluate the safety and feasibility of administering up to 3 cycles of Atezolizumab pre-operatively to patients with resectable urothelial bladder cancer. Note this is the coprimary objective for Cohort B.
 - Endpoint: The percentage of patients with treatment-related adverse events according to CTCAE v5.0 or treatment-related delays in surgery beyond 12 weeks following administration of neoadjuvant treatment with atezolizumab with or without tiragolumab. Note for Cohort A CTCAE v4.0 was used.

Expansion Cohorts

1. To assess the anti-tumor activity of neoadjuvant treatment as determined by pathologic partial response (<pT2N0) assessed at the time of radical cystectomy
 - Endpoint: Percentage of patients with pathologic downstaging (<pT2N0) at the time of radical cystectomy
2. To determine the 2-year relapse-free survival (RFS) rate and median RFS from time of radical cystectomy in patients treated with neoadjuvant therapy
 - Endpoint: 2-year RFS rate and median RFS in ITT population
3. To determine the 2-year overall survival (OS) and median OS from time of radical cystectomy in patients treated with neoadjuvant therapy
 - Endpoint: 2-year OS rate and median OS in ITT population
4. To assess the intratumoral immune response of neoadjuvant by comparing pre-treatment TURBT with post-treatment cystectomy tumor specimens

- Endpoint: Association of tumor and T-cell PD-L1/PD-1 immunohistochemical expression with disease response

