6.9.4 Post-cystectomy/Follow Up Visits

Patients will be followed every 4 weeks (+/- 1 weeks) from the time of cystectomy for 12 weeks, and thereafter every 12 weeks for up to 2 years after cystectomy or until disease progression, death, study termination, or withdrawal from study, whichever occurs first.

- Radiographic imaging should occur every 12 weeks and at end of treatment as outlined in the study calendar.
- The following Central Laboratory tests should be obtained every 12 weeks
 - TBNK blood sample
 - Plasma, serum, and blood sample for PD biomarkers
 - Urine sample for cytokine assessment.

Once all therapy is completed patients should be followed every 12 weeks until the completion of 2 years after cystectomy or until disease progression, death, study termination, or withdrawal from study, whichever occurs first.

Patients who discontinue study treatment prior to cystectomy for reasons other than disease progression (e.g., toxicity) should continue to undergo scheduled tumor assessments until the patient dies, experiences disease progression, withdraws consent, for 2 years from the last dose of study therapy or until the study closes, whichever occurs first.

Patients who start a new anti-cancer therapy (i.e. adjuvant chemotherapy) in the absence of disease progression should continue to be followed for progression according to the protocol schedule of response assessments unless they withdraw consent, experience disease progression, death, study termination, or withdrawal from study, whichever occurs first.

In addition to tests performed per local standard of care, the following procedures will be performed at the Follow Up Visit(s):

- Physical examination
- Vital signs
- Performance Status
- Evaluation of adverse events
 - After initiation of study drug, all adverse events will be reported until 30 days after the last dose of study treatment. After this period, investigators should report any deaths, serious adverse events, or other adverse events of concern that are believed to be related to prior treatment with study drug.
- Concomitant medications

- Pathologic review of tumor response (first follow up visit only)
- Local Laboratory Assessments. Unless otherwise noted, they may be obtained up to 96 hours prior to the visit:
 - Hematology assessment, including CBC with differential and platelet count

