8.3.3 Analysis of Secondary Endpoints

8.3.3.1 Near complete pathologic response rate, 2 year relapse-free survival, 2 year overall survival

Point estimates and 95% confidence intervals of the near complete pathologic response rate, defined as the presence of only pTa or pTis in patients with T2 or greater disease at baseline, the 2 year RFS rate defined from study start until recurrence of disease or death from any cause, and the 2 year overall survival (OS) rate defined from study start until death from any cause, will be obtained for patients enrolled in the study, and compared with the null hypothesis rate (see Section 8.1) separately by using one-sample proportion test. RFS and OS will be obtained by Kaplan Meier method for the ITT population.

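### RFS and OS are set from cystectomy in the objectives but from study start in the analysis; the first origin does not fit all treated patients, and the second leaves progression before surgery unclear

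*Combined protocol and SAP*

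**What the plan says.** Section 2.2 states the RFS objective as "To determine the 2-year relapse-free survival (RFS) rate and median RFS from time of radical cystectomy in patients treated with neoadjuvant therapy" and the OS objective as "To determine the 2-year overall survival (OS) and median OS from time of radical cystectomy in patients treated with neoadjuvant therapy". The abstract matches, for example "median RFS from time of radical cystectomy in patients treated with neoadjuvant therapy". The endpoint line under the RFS objective in 2.2 reads "Endpoint: 2-year RFS rate and median RFS in ITT population", and the OS line names the same population.

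Section 8.3.3.1 uses another origin. For RFS it gives "the 2 year RFS rate defined from study start until recurrence of disease or death from any cause". Its OS rate also begins at study start, with death as the event. The section adds that "RFS and OS will be obtained by Kaplan Meier method for the ITT population".

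ITT appears in the list of abbreviations but is not defined as an analysis set. The nearest definition is in Section 8.3.1, which analyses for safety and efficacy everyone given any part of a dose. It does not require cystectomy, and dosed patients are not replaced. Section 6.9.4 provides for patients who stop before surgery: "Patients who discontinue study treatment prior to cystectomy for reasons other than disease progression (e.g., toxicity) should continue to undergo scheduled tumor assessments". That sentence goes on to set a limit of two years from the last dose. Section 7.1.1 requires resection only for pathologic evaluability.

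**The concern.** Two years from surgery and two years from study start are different quantities, and nothing in the documents says which one will be reported. The population makes this more than a slip of wording. With a cystectomy origin, a treated patient who progresses, dies or declines surgery beforehand has no starting time, although the endpoint lines claim ITT. With a study-start origin every treated patient has a starting time. But recurrence is not defined for a tumour that was never resected, so it is unclear whether progression that rules out cystectomy is an RFS event on the date it occurs.

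In a curative-intent neoadjuvant trial, loss of surgery to progression is something the time-to-event endpoints should be able to show. If origin, event and population stay open, they can be settled after the outcomes are known.

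**Working it through.** The plan gives no rate, event count, power or sample size for RFS or OS, so there is no figure of its own to reproduce.

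**Step 1. The definitions side by side.**

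| | Abstract and 2.2 | 8.3.3.1 |
|---|---|---|
| Origin, RFS and OS | radical cystectomy | study start |
| Population | ITT (in 2.2) | ITT |
| RFS event | not stated | recurrence, or death from any cause |

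The conflict between a cystectomy origin and an ITT population therefore already sits inside 2.2. Section 8.3.3.1 adds the second origin.

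**Step 2. What study start means.** It is not defined. Section 8.3.2.2 counts the 12-week limit on surgical delay from study start, while Sections 5.4 and 5.5 count that limit from first dose. First dose is thus the likely meaning, but the plan does not say so. Section 7.1.2.4 defines PFS and DFS from start of treatment but does not define RFS.

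**Step 3. The gap between the two origins.** With three doses every 3 weeks (weeks 0, 3 and 6) and surgery allowed from 3 weeks after the last dose (5.1.1), the earliest planned surgery is week 9. Section 3.1 sets the latest at week 12. At 4.345 weeks per month, the gap g is 9/4.345 = 2.07 months to 12/4.345 = 2.76 months.
- Two years from study start ends 24 − 2.76 = 21.2 to 24 − 2.07 = 21.9 months after surgery.
- Two years from surgery ends 26.1 to 26.8 months after first dose.

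**Step 4. Effect of the origin alone.** Assume that every patient reaches surgery without an event and that the hazard afterwards is constant. Then S_start(24) = S_cyst(24 − g) = S_cyst(24)^((24 − g)/24). With an assumed S_cyst(24) = 0.60:
- g = 2.07: 0.60^(21.93/24) = 0.627
- g = 2.76: 0.60^(21.24/24) = 0.636

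The shift is +2.7 to +3.6 points. For assumed values of S_cyst(24) from 50% to 80% it is +1.6 to +4.2 points, and median RFS lengthens by 2.1 to 2.8 months.

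**Step 5. Patients who never reach surgery.** Let q be their share and s_q the proportion of them free of an RFS event at two years from study start. Both are assumptions. Then S_start(24) = (1 − q) × S_cyst(24 − g) + q × s_q.
- With S_cyst(24) = 60% and q = 10%: from 0.90 × 0.627 + 0.10 × 0 = 0.564 to 0.90 × 0.636 + 0.10 × 0.30 = 0.603.
- Over S_cyst(24) of 50–80%, q of 5–20% and s_q of 0–30%, the lowest difference from S_cyst(24) is 0.80 × 0.8156 + 0.20 × 0 = 0.652 against 0.80, or −14.8 points. The highest is 0.95 × 0.5415 + 0.05 × 0.30 = 0.529 against 0.50, or +2.9 points.

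**Step 6. Scale.** With 21 patients and a true rate of 60%, ignoring censoring, the standard error is √(0.60 × 0.40/21) = 0.107, or 10.7 points.

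**The case against.** The strongest reply is that this is an inconsistency of wording on unpowered secondary estimates in a single-arm study. OS as written in 8.3.3.1 already suits an ITT population, because every treated patient has a start and can have the event. For OS only the abstract and 2.2 need to change. The pure origin shift of 2.7 to 3.6 points at 60% is small beside a standard error of 10.7. All of that stands, and it limits how serious the point is. It does not remove the contradiction.

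A reader might go further in four ways that the documents do not support.
- *Patients who lose surgery to progression have no RFS event.* Section 8.3.3.1 counts death from any cause, so such a patient who dies within the window is an event. The protocol also uses progression and recurrence loosely: for patients who stop early, 6.9.4 follows to progression and note j of the Study Calendar to recurrence. The event is unclear, not absent.
- *The RFS estimate is biased in favour of treatment.* No direction is shown. Step 5 gives differences of either sign.
- *The definition alone is worth about 6 points.* That figure sets 63.6% against 19/21 × 63.6% = 57.6%. It compares a cohort in which everyone reaches surgery with one in which 2 of 21 do not and all count as failures, so it changes the patients as well as the definition. The share reaching surgery is itself an assumption. In the neoadjuvant pembrolizumab study summarised in Section 1.5, all 50 patients had cystectomy.
- *The gap differs by dose level.* RFS and OS are expansion-cohort objectives. Cohort A expansion uses three atezolizumab doses, every Cohort B level plans three, and no comparison of RFS or OS between dose levels is planned.

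**Conclusion.** The point holds as a contradiction in time origin, combined with a population that the cystectomy origin cannot serve and an RFS event left unclear before surgery. As written, the analysis in 8.3.3.1 does not estimate what the abstract and 2.2 set out to estimate. The two windows end about two to three months apart. Under a constant hazard and an assumed 60% at two years from surgery, the origin alone changes the estimate to 62.7–63.6%. How patients without surgery are handled can matter more, but its size and sign rest on rates that the documents do not give. It should be corrected. It does not affect the sample size.

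**What to change.** In the abstract, 2.2 and 8.3.3.1, measure RFS and OS from first dose in all treated patients, and define ITT in those terms. State that an RFS (event-free) event is the first of progression that precludes cystectomy, recurrence after cystectomy, or death from any cause. Report RFS from cystectomy only as a labelled landmark analysis in patients who were resected.

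The follow-up text also needs reconciling. Section 6.9.6 says that subjects will not be followed for overall survival, although the same paragraph collects survival information, and note l of the Study Calendar follows all patients for survival. If the statement in 6.9.6 is applied, OS cannot be estimated. Section 6.9.6 also ties the end of survival follow-up to cystectomy, so patients without surgery need a stated clock.

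The cost is a few sentences, a short definition of progression before surgery with a place to record it, and possibly a lower reported event-free rate.

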1.2 Treatment of Muscle Invasive Bladder Cancer (MIBC)

Although bladder tumors that are non-muscle invasive are treated with intravesical treatments such as BCG; due to the depth of invasion, intravesical treatments are inadequate for patients with muscle-invasive disease. Therefore, more definitive therapy is needed. Although concurrent chemoradiation may be used for patients who are not surgical candidates or for those desiring bladder preservation, radical cystectomy and bilateral pelvic lymphadenectomy is considered the standard of care. The addition of neoadjuvant cisplatin-based chemotherapy has been associated with both improved overall survival as well as a lower risk of recurrence.² This was illustrated in a randomized Phase III study in which 3 cycles of neoadjuvant MVAC (methotrexate, vinblastine, doxorubicin, cisplatin) chemotherapy increased the pathologic T0 rate from 15% to 38% ($p<0.001$) and was associated with a trend toward increased median survival (46 vs. 77 months, $p=0.06$) when compared to surgery alone.³ Importantly, in this study a pathologic complete response (pCR) to neoadjuvant therapy was associated with both a disease-free and an overall- survival benefit, suggesting that downstaging tumors prior to surgery may confer long term benefit. An analysis of 11 randomized trials of cisplatin-based neoadjuvant chemotherapy concluded neoadjuvant therapy confers a modest survival benefit (OS, hazard ratio [HR] for mortality 0.87, 95% CI 0.78-0.98) corresponding to an absolute survival benefit of 5%, and a modest reduction in the risk of recurrence (HR for recurrence 0.81, 95% CI 0.74- 0.90), corresponding to an absolute disease-free survival benefit of 7%.²

Despite these benefits associated with chemotherapy prior to cystectomy, nationally less than 20% of patients undergoing radical cystectomy for MIBC actually receive neoadjuvant therapy.⁴ Among concerns include advanced patient age, comorbidities, concerns over chemotherapy toxicity, and the modest nature of benefit from chemotherapy.⁶ Similarly there is no neoadjuvant standard of care for patients with marginal renal function, advanced hearing loss, or significant peripheral neuropathy that makes them ineligible for cisplatin therapy. Therefore, novel approaches for these patients are needed.

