A similarly designed study, the PURE-01 trial²⁰, also accrued patients with MIBC to receive neoadjuvant PD-1 checkpoint inhibition. Patients had a predominant urothelial carcinoma histology and clinical (c)T≤3bN0 stage tumor. They received three cycles of pembrolizumab (a PD-1 inhibitor) 200 mg every 3 weeks before RC. The primary end point in the intention-to-treat population was pathologic complete response (pT0). Biomarker analyses included programmed death-ligand 1 (PD-L1) expression using the combined positive score (CPS; Dako 22C3 pharmDx assay), genomic sequencing, and an immune gene expression assay. Fifty patients were enrolled from February 2017 to March 2018. Twenty-seven patients (54%) had cT3 tumor, 21 (42%) cT2 tumor, and two (4%) cT2-3N1 tumor. One patient (2%) experienced a grade 3 transaminase increase and discontinued pembrolizumab. All patients underwent RC; there were 21 patients with pT0 (42%; 95% CI, 28.2% to 56.8%). As a secondary end point, downstaging to <pT2 was achieved in 27 patients (54%; 95% CI, 39.3% to 68.2%). In 54.3% of patients with PD-L1 CPS ≥ 10% (n = 35), RC indicated pT0, whereas RC indicated pT0 in only 13.3% of those with CPS < 10% (n = 15). A significant nonlinear association between tumor mutation burden (TMB) and pT0 was observed, with a cutoff at 15 mutations/Mb. Expression of several genes in pretherapy lesions was significantly different between pT0 and non-pT0 cohorts. Significant post-therapy changes in the TMB and evidence of adaptive mechanisms of immune resistance were observed in residual tumors.

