3.2 Number of Participants

Total Cohort A accrual: Up to 27 participants

- Cohort A Safety Lead-In: 18 participants (already accrued as of October 2020)
- Cohort A Expansion: Up to 9 additional participants may be accrued so that Cohort A expansion group = up to 15 total participants treated at established regimen (6 participants treated at highest administered dose from multi-dose portion + up to 9 additional participants).

Total Cohort B accrual: 21-33 patients

- Cohort B Safety Lead-In: 6-18 patients will be included.
- Cohort B Expansion: 15 additional patients treated with the regimen established during the safety lead-in phase (21 total treated with established regimen)

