- **Near pathologic complete response (near pCR):** Defined as the presence of Ta or Tis disease (or both) in the resection specimen, without evidence of any higher stage disease elsewhere or evidence of tumor in all resected lymph nodes (N0).

All patients will be followed for 2 years post-cystectomy to evaluate for tumor recurrence.

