8.1 Determination of Sample Size and Power Calculation

Cohort A

Multi-dose phase: With 6 patients in each cohort, there will be 80% of power to detect the effect size of 1.5 at significance level of 0.1. For the lowest dose level, a 2-fold increase from pre-treatment to post- treatment is expected, if at the higher dose level, there is more than 3-fold increase, assuming the standard deviation equals 1, then there will be 80% power to detect significant treatment effect on the intratumoral immune response.

Expansion phase: Data from a study of intravesical valrubicin chemotherapy in BCG refractory patients³⁴ demonstrated that a 21% CR rate is achievable at 6 months. Assuming a 5% (null) CR rate for untreated patients at 6 months, 15 patients would be required to observe an improvement to a 36% CR rate at 6 months in response to-PD-L1 therapy (effect size = 0.642), at a significance level of 0.1 with 80% power.

Cohort B

A pT0 rate at cystectomy was observed for ~30% of patients treated with immune checkpoint inhibitors monotherapy based on published Phase II clinical trials. In order to observe an improvement from a 30% CR rate (null hypothesis) to 60% CR rate (alternative hypothesis) with the combination of atezolizumab and tiragolumab a total of 21 patients are required in Cohort B assuming a significance level of 0.05 and 80% power.

Using these assumptions, following a lead in safety phase of 6 patients at a combination regimen that is deemed to be safe based on the criteria outlined above, a further 15 patients will be enrolled at the same regimen. This will make a total of 21 patients to be treated in Cohort B with the intended regimen.

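### Near-pCR, 2-year RFS and 2-year OS are tested against null rates that were set for complete response only (5% and 30%)

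*Combined protocol and SAP*

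**What the plan says.** Section 8.3.3.1 covers three secondary endpoints: near-complete pathologic response (only pTa or pTis left in patients with T2 or greater disease at baseline), the 2-year RFS rate and the 2-year OS rate. Each gets a point estimate and a 95% confidence interval, "and compared with the null hypothesis rate (see Section 8.1) separately by using one-sample proportion test". RFS and OS are also to be estimated by Kaplan-Meier in the ITT population.

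Section 8.1 has two null rates:

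- Cohort A expansion: "Assuming a 5% (null) CR rate for untreated patients at 6 months".
- Cohort B: "improvement from a 30% CR rate (null hypothesis) to 60% CR rate (alternative hypothesis"), based on a pT0 rate of about 30% with checkpoint-inhibitor monotherapy.

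Its only other assumption, for the Cohort A multi-dose phase, is a fold change in immune response, which is not a rate. Section 8.3.2.1 uses the same comparison wording for the primary pT0 rate, where it fits.

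Section 7.1.1 keeps near-pCR apart from pCR: "Defined as the presence of Ta or Tis disease (or both) in the resection specimen", with no higher-stage disease and negative nodes.

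**The concern.** A reference to Section 8.1 for these endpoints leads to a complete-response rate or to nothing. The word separately in the clause does not help, because there are no separate nulls to look up.

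A significant RFS or OS result would show only that more patients are relapse-free or alive at 2 years than would be expected to have a complete response. That says nothing about drug effect. Near-pCR errs the other way: every complete responder counts as a failure, so the better the primary result, the fewer patients can be near-pCR. A two-sided test could report near-pCR as significantly worse than the null in a trial that went well.

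The plan prescribes these tests, so an analyst who follows it will produce and report the p-values.

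**Working it through.** **Inputs.** Cohort B: n=21, null 30%, alpha 0.05 (Section 8.1). Cohort A: null 5%, alpha 0.1 (Section 8.1); Section 3.2 gives "Cohort A expansion group = up to 15 total participants treated at established regimen", six of them carried over from the multi-dose phase, so n is 6 to 15. Sidedness is not stated. Survival anchor (Section 1.2): "trend toward increased median survival (46 vs. 77 months", the first figure being surgery alone. Pathology anchor, the neoadjuvant pembrolizumab trial in Section 1.5: "there were 21 patients with pT0 (42%; 95% CI, 28.2% to 56.8"%) and "downstaging to <pT2 was achieved in 27 patients (54%; 95% CI, 39.3% to 68.2"%).

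**1. The plan's own figures.** Use n = (z_alpha + z_beta)² p1(1−p1)/(p1−p0)², two-sided.

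- Cohort B: (1.960+0.842)² × 0.6×0.4/0.30² = 20.93, so 21.
- Cohort A: (1.645+0.842)² × 0.36×0.64/0.31² = 14.82, so 15.

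Both sample sizes reproduce from the complete-response rates, which confirms what the two nulls were set for.

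**2. Cohort B cutoffs, exact binomial, null 30%.** P(X≥11)=0.0264 and P(X≥12)=0.0087. The test rejects at ≥11/21 (one-sided 0.05) or ≥12/21 (0.025 per tail).

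**3. RFS and OS, Cohort B.** Chance of rejecting, with 24-month status known for everyone:

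| True 2-year rate | ≥11 | ≥12 |
|---|---|---|
| 40% | 17.4% | 8.5% |
| 50% | 50.0% | 33.2% |
| 60% | 82.6% | 69.1% |
| 69.7% | 97.1% | 92.8% |
| 70% | 97.4% | 93.2% |

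The 69.7% is 2^(−24/46), the 2-year OS implied by a 46-month median if survival is exponential. The other rates are assumptions.

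For contrast, exact one-sided 0.05 cutoffs at n=21 against assumed nulls of 50%, 60% and 70% are ≥15, ≥17 and ≥19. As written, ≥11 is enough for every endpoint.

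**4. RFS and OS, Cohort A, null 5%, one-sided 0.1.**

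| n | Cutoff (null tail) | True 40% | True 50% |
|---|---|---|---|
| 6 | ≥2 (0.033) | 76.7% | 89.1% |
| 10 | ≥2 (0.086) | 95.4% | 98.9% |
| 15 | ≥3 (0.036) | 97.3% | 99.6% |

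**5. Near-pCR, Cohort B.**

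- In the pembrolizumab trial, 27−21 = 6 of 50 were below pT2 but not pT0: 12%, exact 95% CI 4.5% to 24.3%. This is an upper figure for Ta/Tis-only disease, because it may include pT1.
- P(X≥11 | 21, 0.12) = 8×10⁻⁶, and 0.005 at 24.3%.
- Lower tail under the null: P(X≤1)=0.0056 and P(X≤2)=0.0271, so the exact two-sided cutoff is ≤1. P(X≤1 | 21, 0.12) = 0.264.
- A successful exact pT0 test needs at least 11 complete responders, leaving 21−11 = 10 patients. That is below the 11 that near-pCR needs, so both cannot succeed.

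**6. If the test is a normal approximation.** The standard error under the null is √(0.3×0.7/21) = 0.10.

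- One-sided: 10/21 gives z=1.76, p=0.039, so the cutoff is ≥10. Rejection at 40/50/60/70% is 30.9/66.8/91.5/99.1%. Here the 10-patients-left argument no longer rules out both tests succeeding.
- Two-sided: cutoffs ≥11 and ≤2. The chance of a significantly low near-pCR at 12% becomes 53.0%.

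**7. Would testing <pT2 against 30% rescue the clause?** No. At 54%, the rate seen with PD-1 monotherapy, Cohort B would reject 64.5% (≥11) or 47.5% (≥12) of the time with no gain from the combination. At the limits of that trial's interval the figures are 15.8% or 7.5% (39.3%) and 96.0% or 90.4% (68.2%). That trial's <pT2 rate is quoted without stating N0.

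**The case against.** The clause looks like wording carried over from the pT0 section, and little depends on it. No sample size, stopping rule or go/no-go decision uses these p-values, and the section already provides estimates, intervals and Kaplan-Meier curves. That stands, and it keeps this a correction to secondary analyses.

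The illustrations also rest on choices the plan does not fix. Section 8.3.3.1 refers to enrolled patients without naming cohorts; n=21 and n=6 to 15 follow from the expansion-cohort heading in Section 2.2. The evaluability rules in Sections 5.9 and 7.1.1 could make the near-pCR denominator smaller than 21. The 70% anchor comes from the surgery-alone arm of a trial of cisplatin-based chemotherapy, whereas this trial enrolls patients who are ineligible for cisplatin or decline it. The two-sided formula is the one that reproduces 21, and with two-sided normal cutoffs the ≥12 column does not apply. These points move the percentages. They do not supply a relevant null, which is missing under every denominator, sidedness and test form.

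On neighboring text, Section 8.3.1 summarizes categorical measurements in general, so <pT2N0 lacks a dedicated analysis with an interval, not every summary. The closing sentence of Section 6.9.6, that subjects will not be followed for overall survival, may mean only no follow-up beyond 2 years.

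**Conclusion.** The concern holds. The three tests in Section 8.3.3.1 use complete-response nulls for quantities that are not complete response, and no suitable null appears in the documents. This follows from Sections 8.1 and 8.3.3.1 alone. The percentages above are illustrations that assume by-cohort denominators, complete 24-month status, the stated true rates and, for the 70% figure, exponential survival and transfer of the surgery-alone median to this population.

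The clause should be corrected before analysis. The primary pT0 test, both sample sizes, the planned estimates and intervals, the Kaplan-Meier analyses and the safety stopping rule are unaffected.

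Three mismatches affect the same endpoints and can be settled in the same edit. They do not add to the seriousness of the null-rate error:

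- RFS and OS start at study start in Section 8.3.3.1 but at cystectomy in Section 2.2.
- The <pT2N0 endpoint in Section 2.2 has no dedicated analysis; Section 8.3.3.1 analyzes only the Ta/Tis category.
- The last sentence of Section 6.9.6 conflicts, on its face, with the 2-year survival contacts in the sentence before it, with the OS endpoint and with study calendar note l.

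**What to change.** Delete the comparison clause in Section 8.3.3.1 for these endpoints. Report Kaplan-Meier 24-month RFS and OS and the pathologic proportions by cohort, each with a 95% confidence interval. If a test is wanted, name a sourced benchmark for each endpoint and, for RFS and OS, test the Kaplan-Meier 24-month estimate against it, since a simple proportion test does not handle censoring.

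In the same edit:

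1. Use one time zero for RFS and OS in Sections 2.2 and 8.3.3.1. ITT patients who never reach cystectomy have no cystectomy date. If study start is chosen, state how their RFS is scored; one option is an event at progression before surgery or at death, otherwise censoring at the last tumor assessment. Analyses from cystectomy can be secondary, in patients operated on.
2. Add an analysis of <pT2N0 with a 95% interval and no 30% null. Keep Ta/Tis-only near-pCR as a separate item if wanted.
3. Remove or clarify the last sentence of Section 6.9.6.

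**Cost.** One deleted clause and three wording changes, with no extra patients. Survival contacts about every 3 months are already scheduled (Section 6.9.6, calendar note l). Section 6.9.4 already continues tumor assessments for up to 2 years from the last dose in patients who stop before cystectomy for reasons other than progression. The Section 6.9.6 horizon is counted from cystectomy, so its wording should also cover unoperated patients. All that is lost is p-values with no useful interpretation.
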